10.3.2 Duration of response

Duration of response is measured from the date that the subject first meets the criteria of objective response (as defined in section 10.1) to the date that the subject progresses, or until death from any cause during the period of disease assessments. For the subjects who are not known to have progressed or died, they will be censored at the date of last disease assessment. For the subjects who receive subsequent anti-cancer therapy, they will be censored at the date of last disease assessment before subsequent anti-cancer therapy. The median survival and corresponding 95% confidence interval will be estimated using Kaplan-Meier method.

10.3.3 Rate of PFS at 1 year

Progression-free Survival (PFS) will be defined as the time from date of the consent signed to the date of documented disease progression or death due to any cause, whichever comes first. The subjects without progression or death will be censored at the date of last disease assessment. For the subjects who receive subsequent anti-cancer therapy, they will be censored at the date of last disease assessment before subsequent anti-cancer therapy. For analysis purpose, 1 month is equal to 30.4375 days; and 1 year (12 months) is defined as 365.25 days. The Kaplan-Meier product-limit method will be used to estimate the 1-year PFS rate, as well as the corresponding 95% confidence interval.

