### **11.7.2 Follow Up after Disease Progression**

Upon disease progression, all subjects in the study will be followed approximately every 12 weeks for survival and the use of subsequent therapy until either death or 12 months after accrual of the study cohort has been completed, whichever occurs first. Information on survival and subsequent anticancer therapy may be collected by phone.

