Subjects (amendment 3 cohorts 1-4) will receive tipifarnib administered at a dose of 400 mg, orally with food, bid for 21 days in 28-day cycles. Food intake is important for tipifarnib bioavailability. The relevance of food intake with tipifarnib administration should be highlighted to study subjects. Subjects may use proton pump inhibitors or H2 antagonists during the treatment portion of this study. However, subjects should be instructed to use antacids (magnesium or aluminum containing products) at least 2 hours before or after intake of oral study drug.

Stepwise 100 mg dose reductions to control treatment-related, treatment-emergent toxicities are indicated in the body of the study protocol. In the absence of unmanageable toxicities, subjects may continue to receive tipifarnib treatment until disease progression. Provisions will be made for the continuation of study treatment in subjects whose disease has not progressed beyond the end of the study, e.g. a single subject treatment protocol.

Disease assessments (bone marrow, hematology and quality of life evaluations) will be performed at screening, and at the Day 25 visit (\pm 5 days) performed during Cycles 2, 4, 6, 9 and every approximately 12 weeks thereafter (Cycles 9, 12, 15, etc.), at the End of Treatment visit and during follow up. As part of the disease assessment at screening and at the Day 25 visit performed during Cycles 2, 4, 6 and 9, bone marrow evaluations will be conducted. Thereafter, bone marrow evaluations will occur during disease assessments in accordance with institutional standard practice. Hematologic assessments, including peripheral blood evaluations and review of transfusion requirements, will be performed at screening and at least monthly until disease progression.

Additional disease or hematologic assessments may be conducted if deemed necessary by the Investigator. The timing of the disease and hematologic assessments should be maintained as much as possible independently of potential treatment cycle delays.

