Determination of disease response in subjects with MDS/MPN will be performed by the Investigator according to the Myelodysplastic/Myeloproliferative International Working Group (MDS/MPN IWG criteria, Protocol Table 9). Similarly, disease progression will also be determined based on the MDS/MPN IWG criteria (Protocol Table 10). Determination of disease response in subjects with AML will be performed by the Investigator according to the International Working Group criteria (Cheson 2003). Similarly, disease progression will also be determined based on the IWG criteria (Cheson 2003).

Upon disease progression, all subjects in this study will be followed approximately every 12 weeks for survival and the use of subsequent therapy until either death or 12 months after accrual of the study cohort has been completed, whichever occurs first. Information on survival and subsequent anticancer therapy may be collected by phone.

Subjects who terminate treatment for reasons other than death or disease progression will be assessed at regular intervals for disease progression (approximately every 2 months through the first 6 months from the start of the subject's participation in this study and every approximately 12 weeks thereafter) and leukemic transformation (monthly blood counts). Disease assessments performed during the first 9 months from the start of the subject's

participation in the study will include bone marrow evaluation. Thereafter, bone marrow evaluations will occur during disease assessments in accordance with institutional standard practice. These assessments will continue until disease progression, withdrawal of subject's consent to study procedures or initiation of another anticancer therapy.

All subjects will be followed-up for safety during treatment and up to approximately 30 days (30 \pm 7 days) after treatment discontinuation or until immediately before the initiation of another anticancer therapy, whichever occurs first. Additional follow up may be implemented until the subject recovers from any emergent treatment related toxicity or the adverse event is considered irreversible by the Investigator. Target organ toxicities will be monitored via clinical and laboratory assessments using the NCI CTCAE v.4.03 criteria.

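### The subsequent-therapy censoring rule for PFS and duration of response is not limited to therapy started before progression, conflicts with the event definition, and read literally would bias both results upward

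*SAP*

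**What the plan says.** SAP 10.3.3 has three statements in sequence:

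1. The PFS event is "the date of documented disease progression or death due to any cause, whichever comes first".
2. Subjects with no event: "The subjects without progression or death will be censored at the date of last disease assessment".
3. Subjects with further treatment: "For the subjects who receive subsequent anti-cancer therapy, they will be censored at the date of last disease assessment before subsequent anti-cancer therapy".

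SAP 10.3.2 has the same structure. Duration of response runs from first response "to the date that the subject progresses, or until death from any cause during the period of disease assessments". Subjects not known to have progressed or died are censored at their last assessment, and the sentence on subsequent therapy is then repeated unchanged.

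The second statement is confined to subjects without an event. The third carries no condition on whether progression came first. Neither section gives an order of precedence, and the legible text of Protocol section 12 has no censoring rule for these endpoints.

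On conduct, SAP 5.2 says that "subjects may continue to receive tipifarnib treatment until disease progression". Protocol 11.7.2 adds: "Upon disease progression, all subjects in the study will be followed approximately every 12 weeks for survival and the use of subsequent therapy".

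**The concern.** A censoring rule has to give one answer per subject. For a subject who progresses and then starts another therapy, the event definition says event and the subsequent-therapy sentence says censored. If the sentence is programmed as written, a documented progression is relabelled as a censored time. The error runs one way only, because events are removed and none are added.

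The 1-year PFS rate and duration of response are both named secondary objectives (SAP 5.1.2). The study is open label and progression is judged by the investigator. A choice of reading made at the programming stage could therefore be made with the results already in view.

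**Working it through.** **Inputs.** The rules come from SAP 10.3.2 and 10.3.3. Treatment and follow-up come from SAP 5.2 and Protocol 11.6 and 11.7.2. The documents give no assumed PFS rate, no median, and no share of subjects who go on to new therapy. There is thus no plan figure to reproduce, and every size below is conditional.

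**Step 1. Apply the rules to each type of subject.**

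| Subject | Event definition | Subsequent-therapy sentence |
|---|---|---|
| No event, no new therapy | censored at last assessment | does not apply |
| Event, no new therapy | event | does not apply |
| New therapy before any progression | no event before the therapy | censored before the therapy |
| Progression, then new therapy | event at progression | censored |

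Only the last row gives contradictory answers about an event that had already been documented.

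**Step 2. Can the last row occur?** Yes. Treatment may run until progression, and all progressed subjects are then followed for subsequent therapy. The data will identify these subjects. SAP 9.3 plans only a listing of subsequent therapy, so no summary table would show how many there are.

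**Step 3. Where would the censoring date fall?** At the progression visit, or later if an End of Treatment assessment (Protocol 11.6) comes between progression and the new therapy. A later date keeps the subject in the risk set longer without an event, so it does not reduce the bias.

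**Step 4. Size in closed form.** Let S be the true 1-year PFS and f the share of all events (progressions and deaths together) that become censored at their own time, unrelated to when they occur. The observed event hazard is then (1 − f) times the true one, and Kaplan-Meier tends to S^(1 − f). Under a constant hazard the median is multiplied by 1/(1 − f).

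| f | S = 0.25 | S = 0.40 | Median multiplied by |
|---|---|---|---|
| 0 | 0.25 | 0.40 | 1 |
| 0.25 | 0.25^0.75 = 0.35 | 0.40^0.75 = 0.50 | 1/0.75 = 1.33 |
| 0.5 | 0.25^0.5 = 0.50 | 0.40^0.5 = 0.63 | 1/0.5 = 2.0 |
| 0.75 | 0.25^0.25 = 0.71 | 0.40^0.25 = 0.80 | 1/0.25 = 4.0 |

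**Step 5. From progressors to all events.** Deaths without progression are also PFS events and cannot be followed by new therapy, so f is smaller than the share q of progressors who start one. A simulation of 200,000 subjects used the planned visits (Day 25 of Cycles 2, 4, 6, 9, 12 and so on), a constant hazard, and first events assumed to be 80% progressions and 20% deaths. The first column of results is also the answer under the corrected rule.

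| Assumed median PFS | q = 0 | q = 0.25 | q = 0.5 | q = 0.75 | q = 1 |
|---|---|---|---|---|---|
| 6 months | 0.28 | 0.37 | 0.48 | 0.61 | 0.78 |
| 12 months | 0.52 | 0.60 | 0.68 | 0.78 | 0.88 |

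Cross-check at 6 months and q = 0.5: f is about 0.8 × 0.5 = 0.4, and 0.28^0.6 = 0.47, against 0.48 simulated. The small gap arises because progressions share visit dates.

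**The case against.** The best defence is that the SAP nowhere states that progressed subjects are to be censored. The event is defined first, as whichever of progression or death comes first, and the disputed sentence follows the no-event rule, so it can be read as one more case for subjects still event-free. It also has a proper use. For subjects who stop treatment without progression, SAP 5.2 says: "These assessments will continue until disease progression, withdrawal of subject's consent to study procedures or initiation of another anticancer therapy". A rule confined to subjects who never have an event would miss those who start new therapy and only then progress or die. Where an End of Treatment assessment follows progression, the literal reading also puts the censoring date after a documented event, which makes that reading less natural.

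Much of this stands. The conventional reading is the more plausible intention. But the defence explains only why the sentence is not confined to subjects with no event at all. It does not explain why the sentence omits the condition that the therapy starts before the event. The SAP supplies no precedence rule that would decide the matter.

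Two further points on the defence side also stand. The documents do not say how many progressors receive further therapy. And the affected endpoints are secondary, with no success threshold: cohort success rests on 4 or more responses in 18 (SAP 5.3.2), ORR is a crude proportion (SAP 10.2), and the hazard ratios and log-rank test sit in the overall survival section (SAP 10.3.4), whose censoring does not use this rule.

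**Conclusion.** Wrong as written, of moderate severity. The sentence conflicts with the event definition in the same section, and followed literally it discards documented progression in anyone who later starts new therapy. The direction is upward for both 1-year PFS and median duration of response. The size runs from zero at f = 0 to very large: an assumed 25% becomes 35%, 50% or 71%, and an assumed 40% becomes 50%, 63% or 80%, at f = 0.25, 0.5 or 0.75. These figures rest on assumed values of S and f, and on switching being unrelated to the timing of progression.

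A reader might go further and infer that the SAP orders the censoring of progressed subjects, that most events would be lost, or that the reported results are inflated. The documents do not support this. The event definition points the other way, no share of progressors starting new therapy is given, and nothing shows which reading was programmed. Nor does the point reach the primary ORR analysis or overall survival.

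**What to change.** In SAP 10.3.2 and 10.3.3, replace the sentence with:

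*Subjects who start subsequent anti-cancer therapy before documented progression or death will be censored at the last disease assessment before that therapy; progression or death occurring before subsequent therapy counts as an event, whatever therapy follows.*

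This keeps the rule for the subjects it suits, including those who switch first and progress later, and states which rule prevails for the rest.

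The cost is one sentence in each of two sections, with no new data. If the conventional rule was intended and programmed, no result changes. If not, the PFS and duration-of-response figures may be less favourable.

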10.3.4 Rate of survival at 1 year

Overall Survival (OS) will be defined as the time from date of the consent signed to the date of death due to any cause. Subjects who are alive or lost to follow-up by the end of study will be censored at the date of last known to be alive, which will be derived from the date reported in vital signs, laboratory, disease assessments, death, study discontinuation, and end of study CRFs. OS will be analyzed using Kaplan-Meier method. Rate of survival at 1 year, along with

the corresponding 95% confidence interval will be estimated in the same manner as 1-year PFS. Median survival with 95% confidence interval will also be reported.

The hazard ratio along with 95% CI (KRAS/NRAS WT vs KRAS/NRAS MUT, and CXCR4/2 High vs CXCR4/2 Low) will be estimated using a Cox proportional hazards model. The KRAS/NRAS MUT and CXCR4/2 Low will be used as the reference groups (ie, denominator of the hazard ratio). A time-to-event hazard ratio less than 1.0 would indicate an KRAS/NRAS WT benefit over KRAS/NRAS MUT or an CXCR4/2 High benefit over CXCR4/2 Low. Additionally, Log-rank P-value will be estimated using Kaplan-Meier method.

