5.3.3 Replacement of Subject

Subjects who do not receive at least one dose of tipifarnib will be replaced. Subjects who do not have at least one post baseline disease assessment will be replaced.

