6. GENERAL ANALYSIS DEFINITIONS

6.1 Study period and visit window definitions

6.1.1 Study periods

The study includes the following time and events schedules: screening (Day -28 to Day -1), Day 1, Day 15, and Day 25 of each cycle (28 days per cycle), End of Treatment visit (30 ± 7 days from the last dose of tipifarnib or immediately before the initiation of any other anticancer therapy), Follow up visit, Follow up contact. A detailed description of the time and events schedule of planned study assessments and visit procedures is outlined in Protocol Table 1.

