6.3 Study populations

6.3.1 Full analysis set

The Full Analysis Set (FAS) is defined as all subjects who received at least one dose of tipifarnib in this study. It is the primary population for the safety analysis

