6.3.2 Per protocol analysis set

The Per Protocol Analysis Set (PPS) includes subjects who received at least one dose of tipifarnib, and have a baseline disease assessment and at least one post baseline disease assessment. It is the primary population for the efficacy analysis.

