10. EFFICACY ANALYSES

The efficacy analyses will be performed on the Per Protocol Analysis Set.

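### One-year survival, and to a lesser extent one-year PFS, is biased upward because time starts at consent and dosed subjects who die before any post-baseline assessment are left out

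*SAP*

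**What the plan says.** **Time origin.** SAP 10.3.4: "Overall Survival (OS) will be defined as the time from date of the consent signed to the date of death due to any cause". SAP 10.3.3: PFS "will be defined as the time from date of the consent signed to the date of documented disease progression" or death. Elsewhere the SAP counts time from treatment: in 6.1.2, study Day 1 is the day of the first tipifarnib dose.

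**Analysis set.** SAP section 10: "The efficacy analyses will be performed on the Per Protocol Analysis Set". Under SAP 6.3.2, PPS subjects must have received a dose and must "have a baseline disease assessment and at least one post baseline disease assessment". SAP 5.3.3 adds: "Subjects who do not have at least one post baseline disease assessment will be replaced". It makes no exception for subjects who die first. Protocol 8.2 agrees with this; protocol 12.1.1 makes the replacement optional.

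**The alternative set.** The Full Analysis Set (FAS) "is defined as all subjects who received at least one dose of tipifarnib in this study" (SAP 6.3.1), but it is named as primary only for safety. No FAS or first-dose version of PFS or OS is planned.

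**Timing.** SAP 6.1.1 gives "screening (Day -28 to Day -1" as the screening period. The first scheduled Day 25 disease assessment falls in Cycle 2, about study Day 53. SAP 5.2 describes these assessments broadly: "Disease assessments (bone marrow, hematology and quality of life evaluations) will be performed at screening". SAP 6.3.2 does not say whether a blood count alone, such as the Day 15 hematology in protocol 11.4, admits a subject to the PPS.

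**The concern.** Two features of the plan act in the same direction on OS.

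1. Only dosed subjects are analysed, so every one of them survived from consent to first dose. Up to 28 days that cannot contain a death still count towards the 365.25-day landmark.
2. A dosed subject who dies before any post-baseline assessment has an OS event by definition, yet is not in the analysed set and is replaced by someone else. The subjects with the worst early outcome are the ones removed.

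PFS shares the first feature. It is less exposed to the second, because a documented early progression is itself an assessment and keeps the subject in as an event. Only deaths before any assessment are lost. For subjects who leave alive without an assessment, the direction of the effect cannot be determined.

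One-year PFS and one-year survival are named secondary endpoints and will be read as outcome on tipifarnib. The report could also contradict itself: safety uses the FAS and lists adverse events leading to death (SAP 11 and 11.1), so an early death could appear there and be absent from the survival curve. The early deaths also drop out of the Cox and log-rank comparisons, which lose events. No bias in the hazard ratios is claimed.

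**Working it through.** The documents give no 1-year rate, event count or early-death rate, so there is no planned figure to reproduce. The direction for OS follows from the text. The size needs assumptions.

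**Inputs**
- Landmark: 365.25 days; 1 month = 30.4375 days (SAP 10.3.3).
- L, days from consent to first dose: 0 to 28 (SAP 6.1.1).
- q, days from first dose to the qualifying assessment: 14 (Day 15 blood count) or 52 (Day 53).
- OS median: 11.7 months, which protocol 5.1.3 cites for an earlier MDS study that included CMML. Medians of 6 and 18 months are assumed for range.
- PFS median: 6 months (assumed).
- Event times: exponential (assumed).

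**OS.** S(t) = exp(−λt), with λ = ln 2 / (median × 30.4375). The true rate is S(365.25). The rate under the SAP is S(365.25 − L) / S(q).

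For 11.7 months, λ = 0.6931 / 356.12 = 0.001946 per day. This gives S(365.25) = 0.491, S(337.25) = 0.519, S(14) = 0.973 and S(52) = 0.904.

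| Case | 1-year OS | Shift (points) |
|---|---|---|
| All dosed, from first dose | 49.1% | – |
| Consent origin only, L = 28 | 51.9% | +2.8 |
| PPS only, q = 14 | 50.5% | +1.4 |
| PPS only, q = 52 | 54.3% | +5.2 |
| Both, L = 28, q = 14 | 53.3% | +4.2 |
| Both, L = 28, q = 52 | 57.4% | +8.3 |

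The share of dosed subjects deleted for early death is 1 − S(q): 2.7% at q = 14 and 9.6% at q = 52. Per 18 dosed, that is 0.5 and 1.7 subjects.

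At other medians, from the mildest case (L = 0, q = 14) to the most extreme (L = 28, q = 52):
- 6 months: true 25.0%, reported 26.4% to 33.9%.
- 18 months: true 63.0%, reported 64.1% to 69.7%.

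As a cross-check, a simulation of 400,000 subjects used the 11.7-month median, a lag uniform on 0 to 28 days and a first assessment uniform on 48 to 58 days, with all earlier deaths lost. It moved OS from 49.1% to 55.9%.

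**PFS.** Let f be the share of PFS events before day q that are deaths without any assessment. The reported rate is S(365.25 − L) / (1 − f × (1 − S(q))). With a 6-month median, S(365.25) = 0.250, S(337.25) = 0.278 and S(52) = 0.821.
- L = 0, f = 0: 25.0%, no shift.
- L = 28, f = 0: 27.8%.
- L = 28, q = 52, f = 0.5: 0.278 / (1 − 0.5 × 0.179) = 30.5%.

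**Direct count, without a survival model.** If 9 of 18 PPS subjects are alive at one year, the rate is 50.0%. Adding back one early death gives 9/19 = 47.4%; adding back two gives 9/20 = 45.0%.

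**Scale.** The exact 95% interval at 9/18 is 26% to 74%.

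**The case against.** The strongest objection concerns size. The +8.3 points require every subject to have the full 28-day lag and every death before Day 53 to be unassessed. An early failure can still enter the PPS through the End of Treatment visit or an additional assessment at the investigator's discretion. With a 14-day lag and half the early deaths deleted (both assumed), the 11.7-month model gives 0.505 / (1 − 0.5 × 0.096) = 53.0%, or +3.9 points. The median is also borrowed from another population and dose, and eligibility limits on performance status and organ function may make early mortality lower than a constant hazard implies. All of this stands as a limit on magnitude: +8.3 is a worst case. None of it reverses the direction for OS.

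The lesser effect on PFS holds only in percentage points. In the upper cases the relative inflation is 30.5/25.0 = 1.22 for PFS against 57.4/49.1 = 1.17 for OS, and the 50% share of unassessed deaths is an assumption. That stands too.

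These are also descriptive rates with no benchmark, the shifts lie inside the sampling interval, and early deaths remain visible in the safety and disposition listings. This lowers the priority. It does not justify leaving in a bias of known direction, because a wide interval does not correct one.

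Finally, counting every unassessed death as a PFS event while censoring unassessed survivors at Day 1 could pull PFS down. The SAP already makes death from any cause a PFS event, so the rule is consistent with its definition, but the revised text must cover subjects who start other therapy before any assessment.

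**Conclusion.** The concern holds. Followed exactly, the SAP overstates 1-year OS whenever there is a lag between consent and first dose or any dosed subject dies unassessed. Under exponential survival with an 11.7-month median, the overstatement is +1.4 points (no lag, Day 15 blood count qualifies) to +8.3 points (28-day lag, nothing before Day 53 qualifies). Exclusion of early deaths contributes +1.4 to +5.2 points on its own, and the consent origin at most +2.8. For PFS with an assumed 6-month median, the range is 0 to +5.5 points.

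The sizes rest on assumed medians, a constant hazard, and an early-death rate and screening lag that the documents do not give. The direction for OS does not depend on the survival model. The point concerns CMML and MDS/MPN, since SAP section 4 leaves AML out of the report. It should be corrected, but it does not affect the ORR decision rule.

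**What to change.** - **SAP 10.3.3 and 10.3.4:** measure PFS and OS from the date of first tipifarnib dose, in the FAS as already defined in SAP 6.3.1.
- **Early deaths:** count a death before any post-baseline assessment as an event for both endpoints.
- **Subjects alive without a post-baseline assessment:** censor at Day 1 for PFS and at the last date known alive for OS. State the PFS rule for those who start other anticancer therapy before any assessment; applying the existing censoring rule also leads to Day 1.
- **PPS version:** keep it as supportive only.
- **SAP 6.3.2:** say which assessment admits a subject to the PPS, in particular whether a blood count alone is enough.

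The cost is SAP wording and programming. No new data are needed, because doses, deaths and last-known-alive dates are already collected. Protocol 12.1.1 names the PPS as the primary efficacy population but does not rule out other sets, so one sentence should record why these two endpoints use the FAS. The reported 1-year rates will be somewhat lower.
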